1. Objective 1: Assess the independent prognostic value of baseline T-cell density, T-cell receptor (TCR) clonality, ctDNA fraction, and mutational load in terms of response in each arm.

We will consider each treatment arm separately. Then for each arm, we will assess whether each of the IHC markers, T-Cell clonality, ctDNA fraction, mutational load and mRNA signatures can be used to identify patients who respond. Under our first objective, we will assess each variable individually. In particular, we will use logistic regression to regress dichotomous response status on each variable, one-at-a-time. Since our primary objective is to develop a classification model for identifying responders, we will estimate standard model classification characteristics including misclassification error, sensitivity, specificity, and AUC for each variable where the threshold for the logistic probabilities for defining predicted responder vs. non-responder will be tuned via leave-one-out cross validation (LOOCV). We will estimate both the in-sample classification characteristics as well as the cross-validated (where the full procedure is cross-validated, with potential nested LOOCV for tuning parameter selection) characteristics with corresponding 95% confidence intervals. The in-sample estimates represent optimistic values while the LOOCV estimates represent pessimistic values such that the smallest lower 95% CI and highest upper 95% CI bound for each characteristic on each variable will provide conservative coverage of the true characteristic value. For Arm 1 (ipilumimab alone), with a sample size of 21 patients, assuming we have 90% compliance on tissue submission, then we will be able to estimate the in-sample or cross validated misclassification error to within 22.5% (95% CI). For Arm 2 (combination therapy), with a sample size of 63 patients and again assuming 90% compliance on tissue submission, then we will be able to estimate the in-sample or cross validated misclassification error to within 13.0% (95% CI).

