We will assess the joint capacity of the IHC markers, T-Cell clonality, ctDNA fraction, and mutational load, and gene expression signatures to identify patients who respond to each therapy. In particular, analyzing each arm separately, we will use the logistic elastic net to model the joint effect on response of the multiple markers and variables simultaneously. We will select the tuning parameters for elastic net via a two-dimensional grid search and LOOCV. We will again estimate the in-sample and cross-validated (of the entire procedure with nested LOOCV for tuning) model classification characteristics and corresponding 95% confidence intervals, again noting that these represent optimistic and pessimistic bounds for each characteristic. Since the elastic net essentially enforces linearity in the effects of the variables, we will also consider the use of alternative strategies, including large margin (e.g. support vector machines) and tree based classifiers in order to accommodate potential nonlinear and potentially interactive effects. Independent of the specific classification method used, for Arm 1, with a sample size of 21 patients and again assuming we have 90% compliance on tissue submission, then we will be able to estimate the in-sample or cross validated misclassification error to within 22.5% (95% CI). For Arm 2, with a sample size of 63 patients, 90% compliance on tissue submission, then we will be able to estimate the in-sample or cross validated misclassification error to within 13% (95% CI)

3. **Objective 3:** Identification of T-cell Poor Subtype(s) Associated with Response

We will first define the range of CD-8+ T-cell density in the tumor sample characterizing a patient as T-cell poor using a supervised approach: this range is currently undefined for patients who have already failed on an anti-PD1 or anti-PD-L1 agent. Specifically, we will consider a range of thresholds for CD8 expression above which the patients are classified as T-cell rich and below which patients are classified as T-cell poor. For each candidate threshold, we will estimate the proportion of responders above and below the threshold. The final threshold defining T-cell poor status will be selected as the threshold which leads to the highest difference in

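### The stated precision for classifier error (13% in Arm 2, 22.5% in Arm 1) does depend on the classification method, leave-one-out error is not a pessimistic bound, and no rule says which classifier is reported

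*Combined protocol and SAP*

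**What the plan says.** Section 18.1c (Statistical Plan), Objective 2, fits a logistic elastic net in each arm, tuned by grid search and leave-one-out cross-validation (LOOCV). It reports in-sample and cross-validated characteristics, "again noting that these represent optimistic and pessimistic bounds for each characteristic". The cross-validation is described as covering the whole procedure, with nested LOOCV named for tuning. Because the elastic net is essentially linear, "we will also consider the use of alternative strategies, including large margin (e.g. support vector machines) and tree based classifiers".

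The precision statement follows: "Independent of the specific classification method used, for Arm 1, with a sample size of 21 patients" and 90% tissue compliance, the team expects to "estimate the in-sample or cross validated misclassification error to within 22.5% (95% CI"). For the other arm it reads "For Arm 2, with a sample size of 63 patients, 90% compliance on tissue submission", giving the ability to "estimate the in-sample or cross validated misclassification error to within 13% (95% CI").

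The labels come from Objective 1: "The in-sample estimates represent optimistic values while the LOOCV estimates represent pessimistic values". Objective 1 also builds an interval from the lowest lower limit to the highest upper limit of the two confidence intervals and describes its coverage as conservative.

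Objective 3 chooses a CD8 cut-off by the largest difference in response, repeats the Objective 2 approach among the T-cell-poor patients, and gives half-widths of 25.2, 23.7 and 23.1% (Arm 1) and 14.6, 13.7 and 13.4% (Arm 2).

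**The concern.** Three statements are open to doubt.

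- **Method independence.** A binomial half-width treats the n leave-one-out errors as n independent trials of one fixed classifier. They come from n overlapping fits, and how strongly they move together depends on the stability of the method. Trees are unstable.
- **In-sample or cross-validated.** The same half-width is attached to both kinds of error, although the plan itself calls the in-sample values optimistic.
- **Pessimistic bound.** Each leave-one-out fit uses n−1 patients, so its expected error is almost that of the full-data model. Being nearly unbiased is not the same as being a bound.

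The plan also does not say how a result is chosen among elastic net, support vector machine and tree, whether all are reported, or whether the choice is repeated in each outer fold. The integrated responder model is a central translational output. An error rate several points too low, with an error bar that is too short, could mislead follow-on work.

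**Working it through.** **1. The plan's figures.** Inputs from Section 18.1c: 21 and 63 patients, 90% tissue compliance. Half-width = 1.96 × √(0.25/n) = 0.98/√n.

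- Arm 1: n = 21 × 0.9 = 18.9; 0.98/√18.9 = 22.5%.
- Arm 2: n = 63 × 0.9 = 56.7; 0.98/√56.7 = 13.0%.
- Objective 3, with n multiplied by 0.80, 0.90 and 0.95: Arm 1 gives 25.2, 23.8 and 23.1%; Arm 2 gives 14.6, 13.7 and 13.4%.

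All agree with the plan to rounding. No feature of the classifier enters the formula.

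**2. Does 13 points hold for each method?** This needs simulation under assumptions that the documents do not give. LOOCV error was compared with the true error in a large set of new patients.

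With n = 57, 12 markers and 25–30% response, LOOCV error lay within 13 points of the truth in 91–98% of data sets for penalised linear models and in 76–86% for a depth-3 tree.

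A second setting used n = 57, 20 independent normal markers, 30% response (the Arm 2 rate in Objective 1) and fixed hyperparameters. With no signal, 141 data sets gave:

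| Reported result | True error | In-sample | LOOCV | Within 13 points | LOOCV below truth |
|---|---|---|---|---|---|
| L1 logistic | 0.380 | 0.213 | 0.386 | 90.1% | 53% |
| SVM (radial kernel) | 0.354 | 0.010 | 0.357 | 92.2% | 55% |
| Depth-3 tree | 0.409 | 0.109 | 0.412 | 77.3% | 50% |
| Lowest LOOCV of the three | 0.373 | 0.084 | 0.328 | 89.4% | 77% |
| Choice repeated in each outer fold | 0.373 | 0.084 | 0.370 | 90.1% | 55% |

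Monte Carlo standard error is √(0.901 × 0.099/141) = 2.5 points near 90% and √(0.773 × 0.227/141) = 3.5 points for the tree.

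**3. In-sample error.** The average gap to the truth is 0.380 − 0.213 = 16.7 points (logistic), 0.354 − 0.010 = 34.4 (SVM) and 0.409 − 0.109 = 30.0 (tree). All exceed 13.

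**4. Is LOOCV pessimistic?** For a single fixed method in Arm 2, mean bias was −0.3 to +0.9 points across scenarios, and LOOCV fell below the truth in about half of data sets.

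**5. If the lowest LOOCV error were reported (Arm 2).** With 20 markers the reported error was 3.4–5.7 points too low. Coverage was 78–87% for the Wald interval, 79–93% for ±13 points and 79–87% for the Objective 1 style interval. With 12 markers the optimism was 2–4 points. In the 12-marker runs at 25% response, the Objective 1 style interval covered 80–81% (Wald limits) or 87–90% (exact limits).

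**6. If the choice is repeated inside each outer fold (Arm 2).** Bias was −0.3 to 0.0 points. Coverage was 87–90% (Wald), 90–93% (±13 points) and 94–95% (Objective 1 style interval).

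**7. Arm 1** (n = 19, 15% response, 20 markers, about 830 data sets per scenario). For fixed methods, ±22.5 points held in 97.8% (SVM) and 86.2–88.5% (tree). For the lowest of three it held in 94.7–95.0%, with bias of −0.8 to −1.2 points. This is weak evidence on optimism. With 18.9 × 0.15 = 2.8 expected responders, data sets with fewer than two responders were dropped, which raises LOOCV error by about 3 points and can hide optimism.

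**The case against.** The strongest reply is that the plan cross-validates the whole procedure and names a lead method, the elastic net. The alternatives are only to be considered, and the stated reason is nonlinearity and interaction, not a lower error. Read that way, step 6 applies and little optimism remains. The half-widths are also a conventional worst case at 50% error; at 25% error the formula gives 1.96 × √(0.25 × 0.75/56.7) = 11.3 points. Most of this stands, and it rules out several stronger readings that a reader might infer:

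- **That the method is chosen outside the nested loop.** The documents do not say so. They name nesting for tuning and are silent on method choice. The defect is a missing rule.
- **That trees or support vector machines in themselves make the error too good.** They do not. Fixed methods were nearly unbiased in Arm 2; the optimism comes from reporting the lowest. Some Wald under-coverage remains without any selection, so selection is not its only cause.
- **That the plan claims conservative coverage for Objectives 2 and 3.** The interval rule and that claim appear only in Objective 1, for single markers, where LOOCV error was within about 1 point of the truth. Objective 2 repeats only the optimistic and pessimistic labels.
- **That 80–90% coverage is a property of the plan.** It depends on the assumed markers, effects and selection rule. Choosing among six variants gave Wald coverage of 56–75%.

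The reply does not rescue the claim that precision is independent of the method, the use of one half-width for in-sample error, or the pessimistic label.

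**Conclusion.** The concern holds in this form. The 13% and 22.5% figures, and those in Objective 3, are plain binomial approximations. Under the simulation assumptions 13 points is roughly right for a penalised logistic model in Arm 2, too short for a small tree (about 76–86% instead of 95%), and far too short for in-sample error. LOOCV error is about unbiased and is not a pessimistic bound.

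An Arm 2 error about 2–6 points too low, with intervals covering roughly 80–90%, is conditional: it follows if the lowest LOOCV error is reported, which the plan neither states nor excludes. Clear optimism was not shown for Arm 1. The effect of choosing the Objective 3 cut-off on response was not simulated; the plan does not say that the cut-off is re-derived in each fold.

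The numbers rest on 12 or 20 assumed markers, assumed effect sizes and particular classifier settings. In the 20-marker runs hyperparameters were fixed rather than tuned, and the inner choice of method used five folds rather than leave-one-out. These are translational objectives, and the primary PFS comparison is not affected. The wording should be corrected because it states a property that the analysis does not have.

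**What to change.** In Section 18.1c:

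1. Delete the Objective 2 clause that makes precision independent of the classification method. Label 13% and 22.5%, and the Objective 3 figures, as binomial approximations for the cross-validated error of a stable penalised model. State that they do not apply to in-sample error or to trees.
2. Remove the word pessimistic as a description of LOOCV in Objectives 1 and 2, and do not carry Objective 1's claim of conservative coverage over to Objectives 2 and 3.
3. Either name the elastic net as the reported classifier and show the others descriptively, or state that the choice of classifier, and the Objective 3 CD8 cut-off, is repeated in every outer fold. In both cases report every method tried.

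The simulated half-widths for trees should not be written into the plan as fixed values, because they depend on the assumptions above. Stratified k-fold should not be prescribed for Arm 1 either: with about three expected responders, more than three folds cannot each contain one.

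The cost is SAP wording and computing time. The reported error may be a few points higher, and the stated precision slightly less favourable.

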11.0 STATISTICAL CONSIDERATIONS

11.1 Accrual Goal

Although the primary objective aims to assess whether combination therapy ipilimumab and nivolumab is superior to single therapy ipilimumab in patients who have previously progressed on anti-PD-1 or anti-PD-L1 therapy, major additional objectives of this study include assessment of key biomarkers and genomic correlatives, particularly for patients who receive combination therapy. This study will use a design in which 63 patients will be randomized to receive combination therapy ipilimumab and nivolumab and 21 patients will be randomized to receive single therapy ipilimumab. Assuming an ineligibility rate of 10% the total accrual goal is 94 patients.

The unbalanced randomization is motivated by the necessity of evaluating the first secondary objective. In particular, the underlying rationale for the combination therapy is that initial progression on PD-1 blockade alone results from poor T cell recruitment. If the combination therapy is superior to single agent ipilimumab, evaluation of this hypothesis by comparing T cell infiltration between patients who have an objective response (confirmed and unconfirmed partial or complete response per RECIST 1.1) and patients who do not have an objective response to combination therapy will elucidate mechanisms that are imperative for design and development of further studies of combination therapy in this population. Thus, unbalanced randomization is necessary to ensure adequate sample size for evaluating this hypothesis. Assuming a response rate of 25% and 90% compliance in tissue and biopsy submission, then we anticipate accruing 14 eligible objective responders and 43 eligible objective non-responders in the combination therapy arm.

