Although our primary analysis will focus on developing classification models, we will also assess the association between response and each individual marker, clonality, mutational load, mRNA expression signature, and ctDNA fraction. The analysis will be again conducted separately by treatment arm. For each of the IHC markers, clonality, and ctDNA fraction, we will test for difference in mean levels between responders and non-responders using two-sample t-tests. We assume we obtain data on 90% of patients and that the response rates are 15% and 30% in arms 1 and 2, respectively. Then at the nominal $\alpha=0.05$ level, we anticipate 80% power to detect a difference in marker level, clonality, or ctDNA fraction between responders and non-responders of 1.9 and 0.83 standard deviations in Arms 1 and 2, respectively. Further, we will also assess whether individual mRNA transcripts and genes are associated with response. Specifically, we will compare the expression between patients who respond and who do not respond using two-sample t-tests again. We will accommodate multiple testing by controlling the false discovery rate. With the same response rate and sample size assumptions as before, and further assuming that 80% of genes are not associated with response, then at the FDR = 5% level, we anticipate 80% power to detect a difference in expression level of 2.43 and 1.33 standard deviations in Arms 1 and 2, respectively. Note that t-tests are used since they can be more powerful than logistic regression, but for all association analyses in this objective and subsequent translational medicine objectives, we will consider the use of alternative approaches, e.g. data transformation, Wilcoxon tests or logistic regression, if there are outliers or influential points.

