proportion of responders above vs. below the threshold. We will also consider un-supervised approaches based on identifying gaps in the distribution of CD8 expression and will tune this according to our supervised results.

After defining the range characterizing patients as T-cell poor, we will restrict further analyses to the patients determined to be T-cell poor. We will then repeat the approach used in Objective 2 to develop a signature identifying T-cell poor patients who respond to therapy. We will again estimate the in-sample and cross validated classifier operating characteristics and construct 95% confidence intervals. Assuming that 90% of patient samples are available for analysis, for Arm 1, we will be able to estimate the in-sample or cross-validated misclassification error to within 25.2%, 23.7%, or 23.1% (95% CI) if 80%, 90%, or 95%, respectively, of patients are determined to be T-cell poor. For Arm 2 we will be able to estimate the in-sample or cross-validated misclassification error to within 14.6%, 13.7%, or 13.4% (95% CI) if 80%, 90%, or 95%, respectively, of patients are determined to be T-cell poor.

We will repeat this analysis using the data collected from blood samples.

References for 18.1

- 2 Morrison C. 'Financial toxicity' looms as cancer combinations proliferate. *Nat Biotechnol* 33:783-4, 2015.

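### Objective 3 sets the T-cell-poor cut by the largest raw response difference over an unbounded range of thresholds; this favours very small groups, and the selection is not written into the cross-validation

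*Combined protocol and SAP*

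**What the plan says.** Under Objective 3 of the statistical plan in Section 18.1c, the investigators say "we will consider a range of thresholds for CD8 expression above which the patients are classified as T-cell rich" and below which they are T-cell poor. For each candidate they estimate the proportion of responders on either side. The rule is then: "The final threshold defining T-cell poor status will be selected as the threshold which leads to the highest difference in" the "proportion of responders above vs. below the threshold".

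The plan does not state the limits of the range, a minimum number of patients per side, any standardisation, any correction for the search, or whether the difference is signed or absolute. An unsupervised alternative based on gaps in the CD8 distribution is mentioned, but it is to be tuned to the supervised result, so it also depends on response.

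Once the cut is set, "we will restrict further analyses to the patients determined to be T-cell poor". The Objective 2 modelling (logistic elastic net with leave-one-out cross-validation, LOOCV) is then repeated in that subset. The only precision figures given are half-widths for misclassification error if 80%, 90% or 95% of patients are T-cell poor.

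**The concern.** The sampling error of a difference in proportions grows sharply when one group is small. A rule that takes the largest raw difference therefore tends to stop where one side holds a handful of patients, because there a proportion can reach 0% or 100% by chance. The apparent difference at the chosen cut is then partly, or under the null wholly, a product of the search.

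The order of steps adds to this. Every patient's response, including that of a patient later held out, helps decide who is in the T-cell-poor cohort. If the cut is not re-selected in each fold, nothing reported corrects for that.

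The plan says this range is undefined in patients who have already failed anti-PD-1 or anti-PD-L1 treatment. The cut from this trial could therefore become a reference definition for later work.

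**Working it through.** **Inputs.**
- Arm 2: "For Arm 2, with a sample size of 63 patients, 90% compliance on tissue submission", so 63 × 0.9 = 56.7, taken as 56 or 57.
- Arm 1: "with a sample size of 21 patients and again assuming we have 90% compliance on tissue submission", so 21 × 0.9 = 18.9, taken as 19.
- Response: 25% in the combination arm (Section 11.1, "Assuming a response rate of 25% and 90% compliance in tissue and biopsy submission"). The translational plan instead assumes "the response rates are 15% and 30% in arms 1 and 2, respectively".
- Non-null CD8 effect: 0.875 SD (Section 11.3).
- Assumption: every cut between ordered CD8 values is a candidate. The documents neither say nor exclude this.

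**The plan's own figures.** Half-width = 1.96 × √(0.25/m), with m = N × 0.9 × share T-cell poor. This gives 25.2%, 23.8% and 23.1% for Arm 1, and 14.6%, 13.7% and 13.4% for Arm 2. The plan's figures are reproduced to within 0.1 point (it states 23.7% for the second Arm 1 value). They are correct for the shares assumed.

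**Why raw differences favour the tails.** With response rate p, the standard error of the difference between groups of size a and b is √(p(1−p)(1/a + 1/b)). For p = 0.25 and 57 patients:
- 28 against 29: 0.433 × √(1/28 + 1/29) = 0.115.
- 3 against 54: 0.433 × √(1/3 + 1/54) = 0.257.
- 1 against 56: 0.433 × √(1 + 1/56) = 0.437.

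If there are 14 responders and the single patient with the highest CD8 is one of them, that cut alone gives 1 − 13/56 = 77 points.

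**Simulation of the stated rule** (20,000 datasets per scenario; difference above minus below; no minimum group):

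| Scenario | 3 or fewer on one side | Mean apparent difference |
|---|---|---|
| Null, n=57, 25% | 59% | 38 points (truth 0) |
| Null, n=57, 30% | 63% | 41 points |
| Null, Arm 1, n=19, 15% | 56% | 30 points |
| 0.875 SD effect, n=57, 25% | 61% | 67 points (24 at a median split) |

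Maximising the absolute difference does not help: under the null at 25% response, 3 or fewer patients remain on one side in 61% of trials (n=57) and the mean difference is 51 points (n=56). With the real effect, a standardised statistic with no floor leaves 3 or fewer on one side in 9% of trials instead of 61%.

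**Link to the planned shares.** Under the null the rule gives an 80-95% T-cell-poor share in only 17% of trials and labels fewer than half of patients poor in 48%. The response rate in the poor group averages about 13% when the truth is 25%.

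**Effect of selecting inside the folds** (1,500 datasets, null, n=56, 25%):

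| Minimum per side | Apparent difference | Cut re-selected in each fold |
|---|---|---|
| None | 0.38 | 0.10 |
| 10% | 0.19 | 0.04 |
| 20% | 0.13 | 0.00 |

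A floor alone leaves optimism; a floor with in-fold selection nearly removes it.

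**The case against.** **The range may not reach the ends.** The plan says only that a range will be considered, so sensible limits may be intended. This stands as a condition on the extremity figures. It does not remove the problem: with a 10% floor the null difference still averages 19 points.

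**A small T-cell-rich group is expected.** The plan allows for 80-95% T-cell poor and explains that most tumours lack T cells. This stands. With the real effect the median poor group is 54 of 57 (94.7%), which a reader might take as failure of the rule; it matches the planned 95% case and is not evidence against it. It also rules out a 20% floor as the remedy: 0.2 × 57 = 11.4, so at least 12 per side, capping the poor group at 45 of 57 (79%), below every share the plan considers.

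**The cross-validation may already include the cut.** Objectives 1 and 2 speak of cross-validating the full or entire procedure, and Objective 3 repeats the Objective 2 approach. No sentence excludes the cut. But the procedure described in Objective 2 contains no cut-point step, and Objective 3 sets the cut and restricts the cohort first. Exclusion is the natural reading of that order, though still an inference.

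**Classifier performance was not shown to be inflated.** A reader might infer that sensitivity, specificity and AUC will be optimistic. A check of a single marker inside the selected subset does not support that. For a marker independent of CD8 the AUC was 0.50. For a marker correlated 0.5 with CD8 it was 0.48 against 0.50 in the full cohort under the null, and 0.58 against 0.62 with a real effect. Raw misclassification error can look better for a base-rate reason: calling everyone a non-responder has an apparent error of about 13% instead of 25% under the null. The full elastic-net procedure was not simulated.

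**The objective is exploratory.** No test or p-value is planned for the cut, and the plan itself describes in-sample estimates as optimistic. This limits the consequences but does not make the selection rule a good one.

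**Conclusion.** The point holds as a weakness in a stated rule. If cuts near the ends are candidates, maximising the raw difference leaves 3 or fewer patients on one side in about 60% of trials whether or not CD8 matters. It produces a 38-point average difference from nothing under the null, and 67 points against 24 at a median split under a 0.875 SD effect. The planned 80-95% share is not assured when CD8 is uninformative. As written, the response difference and the low response rate in the poor group carry selection that nothing corrects.

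The documents do not support saying that the T-cell-poor definition will be mostly noise: that describes the null case, while the trial's premise is that T-cell infiltration is related to response. Nor do they support a claim of inflated discrimination, or any effect on the PFS comparison or the trial's type I error. The figures rest on the sample sizes and response rates in the plan and on an unrestricted search.

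**What to change.** Amend Objective 3 in Section 18.1c as follows.

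1. Choose the cut by a maximally selected standardised statistic (chi-square or likelihood), and state whether the direction is fixed.
2. Pre-specify the candidate range and a minimum group size compatible with the planned 80-95% share. A 5% floor is one example: 0.05 × 57 = 2.85, so 3 patients, allowing a poor group of up to 54 of 57. In Arm 1, 0.05 × 19 = 0.95, so one patient; the floor gives no protection there, and the plan should say how Arm 1 is handled.
3. State that the cut is re-selected inside every outer LOOCV fold. This is needed as well as steps 1 and 2, because a standardised statistic reduces the pull toward small groups under the null but does not remove selection.
4. Report the selected response difference with an optimism-corrected estimate or a permutation-based, selection-adjusted one.
5. Apply the same rules to the repeat analysis on blood samples.

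The cost is a few lines of code and a short change of wording, with no new patients or data. Reported differences and performance will look less favourable.
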